4.3.1.3. Other Exploratory Efficacy Endpoints

Average number of daily urinary incontinence (UI) episodes for subjects with UI at baseline (exploratory)

Average number of urinary incontinence episodes per day will be calculated as the total number of “Accidental Urine Leakage” regardless of the choice of “Main Reason for Leakage” over diary days within the analysis visit window divided by non-missing diary days.

Urgency episodes 50% daily responder (exploratory)

The achievement of at least a 50% reduction from baseline in average daily urgency episodes is a binary variable of 0 (endpoint is not attained) or 1 (endpoint is attained). Subjects will be considered as responders when the endpoint is attained.

Urgency urinary incontinence (UII) episodes daily 75% responder (exploratory)

The achievement of at least a 75% reduction from baseline in average daily UII episodes is a binary variable of 0 (endpoint is not attained) or 1 (endpoint is attained). Subjects will be considered as responders when the endpoint is attained. The endpoint will be analyzed for subjects with UI at baseline.

4.3.2. Patient Reporting Questionnaire Scoring

4.3.2.1. International Prostate Symptom Score

The International Prostate Symptom Score (IPSS) is based on the responses to 7 questions concerning urinary symptoms and 1 question concerning quality of life. Each question concerning urinary symptoms allows the subject to choose 1 out of 6 answers indicating increasing severity of the particular symptom. The responses are assigned points from 0 to 5. The total score can therefore range from 0 to 35 (asymptomatic to very symptomatic).

The questions refer to the following urinary symptoms:

Questions	Symptom	Subscale Category
1	Incomplete emptying	Voiding
2	Frequency	Storage
3	Intermittency	Voiding
4	Urgency	Storage
5	Weak Stream	Voiding
6	Straining	Voiding
7	Nocturia	Storage

Question 8 refers to the subject’s perceived quality of life (QoL). The answers to the single question to assess the quality of life this question range from “delighted” to “terrible” or 0 to 6.

Raw scores for each scale will be calculated as the sum of responses to all the questions within the scale, with missing values imputed as the average value over the scale if <50% of the scale items are missing. If $\geq 50\%$ of the items are missing, no scale score will be calculated, and the subscale score will be considered missing.

To transform the raw scores to a unified score ranging from 0 to 100, the following algorithms are used to derive the corresponding score at baseline, Week 12 and Week 24.

- For the Symptom Bother Score, the transformed score is:

$$score = \frac{(sum\ of\ actual\ score - lowest\ possible\ score)}{range} \times 100 = \frac{sum\ of\ actual\ score - 8}{40} \times 100$$

For Symptom Bother, higher scores correspond to the symptoms having a larger bother and lower scores represent a lower amount of bother due to symptoms.

- For the Coping, Concern, Sleep, Social Interaction, and Total HRQL Scores, the transformed score is:

$$score = \frac{(highest\ possible\ score - sum\ of\ actual\ score)}{range} \times 100$$

In this case, higher scores correspond to a higher quality of life and lower scores represent a lower quality of life.

[figure not shown]
4.3.2.3. [REDACTED]

[REDACTED] covers 5 dimensions of quality of life: mobility, self-care, usual activities, pain/discomfort, anxiety/depression, with respondents selecting one of 5 responses for each dimension. Each dimension has 5 levels: no problems, slight problems, moderate problems, severe problems and extreme problems. The subject is asked to indicate his/her health state by ticking the box next to the most appropriate statement in each of the five dimensions. This decision results in a 1-digit number that expresses the level selected for that dimension. The digits for the five dimensions can be combined into a 5-digit number that describes the patient's health state. The 5-digit number will be mapped to an index value using the crosswalk link function for the US value set based on the published [REDACTED] [4] at baseline, Week 12 and Week 24. At Week 12 and Week 24, the Pareto Classification of Health Change will also be assessed, which classifies health state relative to baseline:

- Health state is better if it is better in at least one dimension and no worse in any other dimension
- Health state is worse if it is worse in at least one dimension and no better in any other dimension
- Health state is unchanged if it all dimensions remain the same

- Health state is mixed if it is better in at least one dimension and worse in at least one dimension.

[REDACTED] also includes a visual analog scale (VAS) to capture a patient's overall health rating.

4.3.3. Study Day and Duration

Study day is relative to the start date of the double-blind treatment. This is used to describe the relative time of an event or assessment that happened during the study. The first day of the study is defined as the day a patient first receives either vibegron or placebo in the double-blind treatment period. This is expected to be the same day as the randomization as Day 1. There is no study Day 0 defined in the study.

- For event or assessment occurring on or after the first dose of double-blind treatment date:
Study day = Date of event or examination – date of first double-blind treatment + 1
- For event or assessment occurring prior to the first dose of double-blind treatment date:
Study day = Date of event or examination – date of first double-blind treatment

A duration between any two dates (such as AE duration) expressed in days will be calculated using the following convention:

- Duration = Later date – earlier date + 1

4.3.4. Baseline and Change from Baseline

In general, the last recorded value on or prior to the date of randomization will serve as the baseline measurement for efficacy endpoints while the last recorded value prior to first double-blind dose of study treatment will serve as the baseline measurement for safety endpoints. The mean of multiple values will be used as baseline for the following situations:

- If multiple measurements are scheduled on the same baseline day (i.e., blood pressure)
- If multiple measurements are collected on the same baseline day without the time or “repeat” status to differentiate the records

For efficacy endpoints derived from the Bladder Diary, the baseline will be the average value over the diary days in the baseline analysis visit window.

Change from baseline will be calculated as the post-baseline value minus the baseline value. Percentage change from baseline will be calculated as the change from baseline divided by the baseline value, multiplied by 100. If either the baseline or post-baseline value is missing, then change from baseline and percentage change from baseline will be set to missing.

4.3.5. Pre-existing and Baseline Hypertension

Pre-existing Hypertension will be assigned based on a search of a subject’s medical history for the presence (Yes) of any or absence (No) of all the following coded terms:

- Accelerated hypertension
- Diastolic hypertension
- Essential hypertension
- Hypertension
- Hypertensive crisis
- Hypertensive emergency
- Hypertensive heart disease
- Malignant hypertension
- Malignant hypertensive heart disease
- Secondary hypertension
- Supine hypertension
- Systolic hypertension

Baseline Hypertension will be assigned based on a subject’s baseline vital signs:

- Visit average SBP \geq 140
- Visit average DBP \geq 90

5. STUDY SUBJECTS

5.1. Subject Disposition and Withdrawals

Subject disposition will be summarized by treatment arm for the screened, run-in and randomized subjects. The summary table will present the frequency and percentage of subjects in each of the analysis sets and those who discontinued the study prematurely along with the primary reasons for discontinuation.

For the summary for the randomized subjects, the following additional categories will be presented as well; randomized, received treatment with study drug, did not receive treatment with study drug, completed treatment with study drug, discontinued treatment with study drug (and reason), discontinued treatment with study drug but completed study follow-up, completed study, and withdrawn from study (and reason).

The frequency and percentage of subjects with at least one major Protocol Deviation (PD), major PD by classification and reasons/category for PD will be summarized by treatment arm for the FAS. Inclusion in each of the analysis sets (SAF, SAF-Orth, SAF-UDS, UES, FAS, FAS-I, PPS, PPS-I), and any reasons for exclusion will be summarized by treatment arm for the Randomized Set.

Screen Failure, Run-in and Double-Blind Period disposition, with reasons for discontinuation of study will also be listed if applicable, including the date of discontinuation.

Eligibility criteria, screening failures (including date and primary reason for failure), and informed consent (protocol version, informed consent version date and date signed) will be listed for all patients screened.

A summary of randomized subjects by country and investigator will be provided. Randomization details will also be listed, including the date of randomization, randomization number and randomization strata.

5.2. Demographic and Baseline Characteristics

All demographic and baseline characteristic data will be summarized by treatment group using descriptive statistics for all subjects for each of the following analysis sets: SAF, SAF-Orth, UES, PPS-UES, FAS, FAS-I, PPS and PPS-I.

The summary table will include Sex, Ethnicity and Race (US and non-US), Prior Anticholinergic Use (Yes/No), Prior Beta-3 agonist Use (Yes/No), Diabetes Mellitus (Yes/No), Baseline Hypertension (Yes/No), Pre-existing Hypertension (Yes/No), Age category 1 (<55 , ≥ 55 to <65 , ≥ 65 to <75 , ≥ 75 years), Age category 2 (<65 , ≥ 65 years), Age category 3 (<65 , ≥ 65 to <75 , ≥ 75 to <85 , ≥ 85 years), treatment with alpha blocker, treatment with 5-ARI, baseline average micturition episodes per day (≤ 12 vs > 12), Alpha blocker use with or without 5-ARI (with vs without), Urinary Incontinence (yes or no) and IPSS total score. Stratification factors will be summarized both as randomized and corrected if any misstratification was present.

Prior Anticholinergic Use and Prior Beta-3 agonist Use will be calculated from all prior medications documented on the Prior and Concomitant Medications electronic case report form (eCRF).

Pre-existing and Baseline hypertension are defined in section 4.3.5.

Age (years), height (cm), weight (kg), BMI (kg/m²) captured at Screening, and baseline IPSS total score will be summarized as continuous variables.

Unless otherwise stated, percentages will be calculated out of the number of patients in the given analysis set.

All demographic data will be listed.

5.3. Other Baseline Characteristics

The data from the 3-day bladder diary during run-in period (reviewed at Visit 3 Baseline visit) prior to first dose of double-blind medication will be used as baseline for each subject. This includes average number of daily micturition episodes, average number of daily urgency episodes, average number of nocturia per night, average number of daily urge urinary incontinence episodes, and average volume voided per micturition. In addition, the baseline IPSS Storage score, prostate volume, Qmax (maximal urinary flow) at baseline as determined by uroflowmetry (see section 7.7 for details), and baseline post-void residual urine will be presented. These will be summarized by treatment group and overall using descriptive statistics for continuous data for all subjects in FAS, FAS-I, PPS and PPS-I analysis sets.

5.4. Medical History and Concomitant Disease

Descriptions of medical history findings will be coded using Medical Dictionary for Regulatory Activities (MedDRA) version 22.0 or higher.

A disease or illness reported as medical history without a start date will be included in medical history without a date assigned. Medical history will be sorted by descending overall frequency, by system organ class (SOC) and preferred term (PT) in the summary table. Medical history data listings will be sorted by treatment, subject number, start date, SOC and PT. The SAF will be the analysis set for medical history data.

5.5. Procedures

Procedures will be coded using Medical Dictionary for Regulatory Activities (MedDRA) version 22.0 or higher.

Prior procedures are defined as procedures with a start date prior to the first dose of double-blind treatment. Concomitant procedures will be defined as procedures started on or after the first dose of double-blind medication but prior to the last dose of the double-blind medication + 5 days, or started prior to double-blind medication and were ongoing during the double-blind period. Post procedure is any procedure initiated after last dose of double-blind medication + 5 days (See Table 2). Partial procedure start dates will be imputed as detailed in 4.2.3.

All procedures will be listed for the SAF population, sorted by treatment, subject number, start date, SOC and PT, with indicators of prior and concomitant status.

5.6. Prior and Concomitant Medication

Prior and concomitant medications will be coded using the World Health Organization (WHO) Drug B3-Sept Format, 2018 version or higher. Except for Prior OAB medication, the number and percentage of subjects taking prior medications and concomitant medications will be summarized overall by ATC (Anatomical Therapeutical Chemical) Levels 2 and 4 for all subjects in the SAF. Prior OAB medications will be summarized by ATC Levels 2, 4 and Preferred Term in the SAF. Prior medications OAB medication and concomitant medications will be listed for all subjects in the SAF.

5.6.1. Prior Medication

Prior medications are defined as those medications taken prior to the first dose of double-blind treatment. The prior non-OAB and prior OAB medications will be summarized separately.

The following criterion will be used for selecting prior OAB medication:

Table 6: OAB Medication Selection

Class	Variable Selected	Selection
Anticholinergics	Preferred Term	darifenacin, fesoterodine, fesoterodine fumarate hyoscyamine, oxybutynin, oxybutynin hydrochloride, propantheline, solifenacin, solifenacin succinate, tolterodine, tolterodine l-tartrate, trospium, trospium chloride
Beta-3 adrenergic agonists	Preferred Term	mirabegron, vibegron, solabegron

5.6.2. Concomitant Medication

Concomitant medications will be defined as medications started on or after the first dose of double-blind medication but prior to the last dose of the double-blind medication + 5 days, or started prior to double-blind medication and ongoing during the double-blind period. Post medication is the medication taken after the last dose of double-blind medication + 5 days (See Table 2). Partial medication start dates will be imputed as detailed in 4.2.3.

Non-OAB and OAB concomitant medications will be summarized separately.

5.7. ECG

12-Lead ECG data will be collected at the screening visit only. All data collected will be listed.

5.8. Prostate Volume Measurements

Prostate volume is measured at Screening or historically within 12 months of screening via ultrasound. All prostate volume measurements will be listed.

5.9. Treatment Exposure

The duration of exposure during the double-blind treatment period will be expressed as the time in days from the first dose as recorded on the Study Drug Administration CRF page through to last treatment day (inclusive) as recorded on the End of Treatment CRF page, excluding any days where it is recorded that an interruption has occurred on the AE CRF page or gaps in the study drug log. If no dose was witnessed at the baseline visit, the date of baseline study drug dispensation + 1 will be used. If no last treatment date is recorded, it will be imputed as the minimum of the date of the last visit on the study and the date when last dispensed study treatment was scheduled to be exhausted (last dispensation date + number of doses dispensed).

Gaps in the study drug log will be determined by comparing the dispensation date of a record to the previous dispensation date (where multiple bottles may have been dispensed). If one bottle was dispensed, then the gap is measured from study day of previous dispensation + 32; if two bottles were dispensed then the gap is measured from study day of previous dispensation + total number of pills dispensed.

Interruption in days = date interruption stated – date interruption stopped + 1

The duration is calculated by the following formula:

Duration (days) = date last double blind dose – date first double blind dose – interruption days + 1

Duration of exposure will be summarized by treatment group and overall for the SAF using summary statistics for continuous variables. Total drug interruption days due to AE and gaps in the study drug log will also be summarized. A listing will present the treatment start and end date together with the date of interruption, and the overall duration of exposure.

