3.2. Violations and Deviation

Subjects who do not meet eligibility criteria but are still randomized will be analyzed according to the analysis sets described in Section 3.1.

Major protocol deviations are considered to have major impact on subject safety, efficacy or the validity of the study data.

Patients with major efficacy protocol deviations will be excluded from the PPS and PPS-I under the assumption that the deviation may have an impact on the efficacy analysis, and from PPS-UES under the assumption that the deviation may have an impact on the urodynamics analysis. This may include, but is not limited to the following:

- Subjects who do not meet the following inclusion criteria:
 - On a stable dose of alpha blocker
 - Average frequency of ≥ 8 and ≤ 20 micturitions per day in the baseline diary
 - Average frequency of ≥ 3 urgency episodes per day in the baseline diary
 - Average frequency of ≥ 2 nocturia episodes per night in the baseline diary
- Subjects who meet any of the following exclusion criteria:
 - Total 24-hour urine volume output of >3000 mL based on any baseline diary day
 - History of prostate surgery
 - Subject started using diuretics within 28 days prior to screening
 - Nocturnal Polyuria ($> 1/3$ of total urine output per 24 hours occurring at nighttime) assessed on any day of the baseline diary
 - Has received an intravesical or intraprostatic treatment with any botulinum toxin, resiniferatoxin, or capsaicin within 6 months prior to screening
 - Use of any prohibited anticholinergics or beta-3 adrenergic agonists as detailed in protocol section 10.6 within 28 days prior to screening
- Concomitant use of prohibited medications as detailed in protocol section 10.6
- $<70\%$ Investigational Product [IP] compliance from Baseline through Week 12
- Visit delay at or prior to Week 12 causing more than 14 days without IP
- Failed to complete any diary day for an expected Week 12 diary within Study Day 68-102 [PPS and PPS-I only]

Exclusion from per-protocol analysis is noted for each protocol deviation in the Protocol Deviation specifications.

The final list of major protocol deviations will be finalized and documented before database lock except for the deviation of wrong treatment which will be confirmed upon study unblinding. All major protocol deviations related to efficacy will be finalized prior to unblinding. Only major protocol deviations will be summarized and listed in the Clinical Study Report (CSR).

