4.2.3. Premature Withdrawal and Missing Data

All data collected in the study database after the subject’s cessation of study treatment should be included in summary and analysis. Data of subjects who withdraw after the screening examination or are not treated will only be listed. Assessments taken after the End of Study visit date for subjects continuing on to study URO-901-3006 will not be included in analysis or listings for study URO-901-3005; it will be included in datasets to support inclusion in analysis of study URO-901-3006.

If any visits are missing diary data, no explicit missing data imputation will be performed for the primary analysis of change from baseline since a mixed model for repeated measures (MMRM) will be applied to change from baseline analysis. If time to bed or time to awaken the next morning is missing from a diary day, the average of non-missing days for that subject at that visit

will be used. If no visit average bedtime or time of awakening is calculable, no nocturia measurements will be calculated for that subject at that visit.

Missing items from the subject reported outcomes (PROs) will be handled according to the respective measure instructions as described in Section 4.3.2.

Missing return dates from the study drug log will be imputed as the day of the subsequent drug dispensation, end of treatment visit, or subject discontinuation in the study, whichever is first. Non-return of IP will be considered taken per protocol for calculation of treatment compliance but will be noted in the listing of study medication.

If the first dose of double-blind study medication is not witnessed, the start of medication will be imputed as the day after the drug was dispensed.

In general, missing safety data will not be imputed and only observed values will be analyzed.

If the relationship of an AE record (“Relationship to investigational product” on AE CRF) is missing this AE will be considered “Probably Related” to the study treatment. If the AE intensity is missing every effort should be made to acquire the information from the investigator. “Severe” will be assigned to a missing intensity for reporting purposes.

The general imputation rules of partial missing date and time for both AE and concomitant medication is detailed below:

Dates missing the day of the year will adhere to the following conventions:

- The missing day of onset date will be set to:

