5.10. Treatment Compliance

Study treatment compliance (%) will be calculated as the actual number of doses divided by the expected number of doses, multiplied by 100 and summarized by treatment group and double-blind treatment period.

These numbers will be determined by the number of tablets dispensed and returned unused by the subject. Where no treatment bottle is returned, and thus the actual number of doses is

unknown, it will be assumed that the subject took medication as directed until their supply was exhausted. Imputed values will be clearly noted in the listing.

The expected number of doses is the same as the calculated duration of exposure detailed in section 7.1.

Overall compliance will be calculated for run-in and the double-blind treatment period, respectively.

$$\text{Overall Compliance (\%)} = \frac{\text{Number of doses taken}}{\text{Expected number of doses}} \times 100\%$$

The number of doses taken is summed from values recorded on the drug accountability CRF. If number of doses taken is missing for a log line within the drug accountability CRF, it will be imputed as the minimum of (number of doses dispensed, subsequent dispensation date – current dispensation date).

Treatment Compliance will be summarized for the SAF and FAS population. Additionally, the number and percentage of subjects within each treatment with compliance in the following categories will be provided: <80%, 80 – 120%, and >120%. All data will be listed.

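### With no recorded last treatment date and an unreturned final supply, SAP 5.9 and 5.10 end dosing on different days, which inflates compliance and weakens the <70% per-protocol rule

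*SAP*

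**What the plan says.** **Exposure (SAP 5.9).** Exposure runs to the "last treatment day (inclusive) as recorded on the End of Treatment CRF page". Only if that date is absent does a substitute apply: "it will be imputed as the minimum of the date of the last visit on the study and the date when last dispensed study treatment" runs out (last dispensation date plus doses dispensed).

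**Compliance (SAP 5.10).** Compliance is doses taken over doses expected. For the denominator: "The expected number of doses is the same as the calculated duration of exposure detailed in section 7.1". Section 7.1 covers adverse events; the exposure rule is in 5.9. For the numerator, where a bottle does not come back, "it will be assumed that the subject took medication as directed until their supply was exhausted". A missing dose count on a log line is limited to the smaller of the tablets dispensed and the days to the next dispensation.

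**Missing data (SAP 4.2.3).** "Non-return of IP will be considered taken per protocol for calculation of treatment compliance but will be noted in the listing of study medication". The same section imputes a missing return date as the earliest of the next dispensation, the end-of-treatment visit and discontinuation.

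**Per-protocol set (SAP 3.2).** Compliance under 70% from Baseline through Week 12 is a listed ground for exclusion. So is having no diary day on Study Days 68–102 where a Week 12 diary was expected.

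**TEAE window (SAP Table 2 and 7.1).** It closes 5 days after the last dose, or at rollover to the extension study if that comes first. Neither place says which date applies when the last dose is unrecorded.

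**The concern.** Take a man who collects a bottle, is never seen again, and has no date on the End of Treatment page. His last visit falls before that bottle would be empty, so 5.9 ends his exposure at the visit. SAP 5.10 credits him with the whole bottle, all of it to be taken from that day on, and divides by an exposure that stops there. Numerator and denominator rest on contradictory assumptions about the same tablets. The limit based on the next dispensation does not help, because a final dispensation has none.

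Two uses of the figure are exposed. The compliance tables include a category above 120%, and men who were simply lost could appear there as over-takers. The 70% rule is meant to remove poor compliers from the PPS and PPS-I, and an uncollected bottle can lift such a man over the line.

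**Working it through.** The SAP states no figure for this situation, so there is none to reproduce. The check applies its rules directly.

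**Inputs**
- Visit days: Baseline 1, Week 2 15, Week 4 29, Week 8 57, Week 12 85, Week 20 141 (Protocol 1.3 and 1.4).
- 32 tablets per bottle (Protocol 6.1).
- Week 12 in Part 2: two bottles (64 tablets) assumed, because the next dispensing visit is Week 20 and SAP 5.9 foresees two-bottle dispensing. One bottle is shown as well.
- Assumed: nominal visit days, no recorded last treatment date, final supply not returned, no interruptions or log gaps, and a fraction *a* of the earlier daily tablets actually taken.

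**Formulas**, with V the last visit day, D the day of the final dispensation, T its tablets, and P = D − 1 the earlier dosing days:
- Last dose L = min(V, D + T)
- Expected doses E = L − 1 + 1 = L
- Compliance C = (aP + T)/E
- C exceeds 100% when a > (E − T)/P, and 120% when a > (1.2E − T)/P

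| Last visit | T | P | C at a = 1 | Above 100% if a exceeds | Above 120% if a exceeds |
|---|---|---|---|---|---|
| Baseline | 32 | 0 | 32/1 = 3200% | always | always |
| Week 2 | 32 | 0 | 32/15 = 213% | always | always |
| Week 4 | 32 | 28 | 60/29 = 207% | always (a = 0 gives 32/29 = 110%) | 2.8/28 = 10% |
| Week 8 | 32 | 56 | 88/57 = 154% | 25/56 = 45% | 36.4/56 = 65% |
| Week 12, two bottles | 64 | 84 | 148/85 = 174% | 21/84 = 25% | 38/84 = 45% |
| Week 12, one bottle | 32 | 84 | 116/85 = 136% | 53/84 = 63% | 70/84 = 83% |
| Week 20 | 32 | 140 | 172/141 = 122% | 109/140 = 78% | 137.2/140 = 98% |

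**The 70% rule**, if the 5.10 method is used for Baseline to Week 12:
- Lost after Week 4: exclusion needs 28a + 32 < 0.7 × 29 = 20.3, which is impossible. With the visit at Day 33, the late edge of the ±4-day window, a man with no earlier doses still scores 32/33 = 97%.
- Lost after Week 8: exclusion needs 56a + 32 < 0.7 × 57 = 39.9, so a < 7.9/56 = 14%. A man 20% adherent scores 43.2/57 = 76%; one 50% adherent scores 60/57 = 105%.
- The Week 12 and Week 20 rows do not bear on this rule, because those tablets are for use after the interval.

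**The case against.** Several limits are fair and stand.

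- **Scope.** A reader might infer that every man lost to follow-up is affected. The imputation applies only when the End of Treatment page has no date. The documents do not say how many men would lack both that date and a returned bottle.
- **Size.** A reader might infer that compliance always passes 100%, or that lost men always land above 120%. The first is certain only for a last visit through Week 4 at nominal days. The second needs about 98% earlier adherence for a man lost after Week 20.
- **SAP 4.2.3.** Counting unreturned drug as taken per protocol, with a return date no later than discontinuation, can be read as a limit on doses. That reading conflicts with 5.10, which says exhaustion. It makes the position ambiguous without resolving it.
- **Per-protocol set.** The SAP gives no formula for compliance to Week 12, so using 5.10 there is an assumption. Men lost before Week 12 may already fall to the diary rule, but the SAP does not define when a Week 12 diary is expected. Membership is settled at blinded review.
- **TEAEs.** A reader might infer that events during assumed dosing are wrongly left out. With the 5.9 date, a Week 8 loss would close the window at Day 57 + 5 = 62, while assumed dosing runs to Day 57 + 32 − 1 = 88, leaving 26 days uncovered. However, neither Table 2 nor 7.1 adopts the 5.9 date. Few events would be known once contact is lost, and any reported would still be in the all-AE listing. This is an unstated rule, not a shown error.

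**Conclusion.** The point holds in a limited form. For a man with no recorded last treatment date whose final supply is not returned, the stated rules inflate compliance whenever the last visit precedes exhaustion. SAP 4.2.3 does not clearly agree with 5.10, and the denominator's cross-reference points to the wrong section.

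At nominal visit days the figure always exceeds 100% for loss through Week 4. Later it does so once earlier adherence passes about 45% (Week 8), 25% (Week 12, assuming 64 tablets) or 78% (Week 20). On the further assumption that 5.10 governs the Baseline-to-Week 12 interval, the 70% rule has no force for loss after Week 4 and catches only men below about 14% adherence after Week 8.

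The consequences are limited to the compliance tables and the supportive per-protocol analyses. Men wrongly kept would add Week 2–8 data to the per-protocol MMRM. Their Week 12 value would be imputed in the multiple-imputation ANCOVA, which SAP 6.1.2.2 also runs on the per-protocol set. The primary FAS analysis does not use compliance and is unaffected. The change is worth making because the rules as written give impossible values and the repair is small.

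**What to change.** 1. In SAP 5.10, for an unreturned final dispensation, count doses as min(tablets dispensed, last-dose date used in the denominator − dispensation date + 1). The +1 is needed because exposure is inclusive; without it, a man lost after his witnessed Baseline dose scores 0/1 = 0%.
2. Define Baseline-to-Week 12 compliance for SAP 3.2 by the same rule, with doses and days both cut at Week 12 or at the last-dose date if earlier.
3. Align SAP 4.2.3 with this, and change the cross-reference in 5.10 from 7.1 to 5.9.
4. Separately, state in Table 2 and SAP 7.1 which last-dose date closes the TEAE window when none is recorded. If it deliberately differs from the compliance date, say so.

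With item 1, a full complier scores (28 + 1)/29 = 100% after Week 4 and (56 + 1)/57 = 100% after Week 8. A half-adherent man scores (14 + 1)/29 = 52% and (28 + 1)/57 = 51%, so the 70% rule works again.

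The cost is a few sentences and a few lines of code, best settled before per-protocol membership is fixed at blinded review. One limit remains: intake from the open supply before the last visit is still assumed, so a man last seen at Week 2 scores 15/15 = 100% whatever he took.
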